## 9.2 Discussion of Study Design

This is a Phase 4, multi-site, open-label, single arm study to assess efficacy and safety of pegloticase in adult subjects with uncontrolled gout who have undergone kidney transplantation.

During the pre-marketing Phase 3 studies for pegloticase, subjects with organ transplant were excluded from participation; however, subjects with renal impairment were included, and showed comparable safety and efficacy as the general study population. Kidney transplant recipients with uncontrolled gout have the potential to benefit from the ability of pegloticase to rapidly deplete urate deposits, even when urate excretion is impaired. In addition, immunosuppressive agents to prevent rejections have the potential to thwart the formation of ADA against pegloticase, thereby preserving its effectiveness and decreasing the risk of infusion reactions.

This study will test safety and effectiveness of pegloticase (administered 8 mg via IV infusion every 2 weeks, consistent with the current pegloticase prescribing information) in kidney transplant subjects with chronic gout refractory to conventional urate lowering therapy.

Prospective use of sUA stopping rules, with pegloticase treatment cessation (but study continuation) when a subject has a pre-infusion sUA level >6 mg/dL on two consecutive study visits, will also help confirm the value of this approach to reduce IR risk.

### 9.3 Selection of Study Population

#### 9.3.1 Inclusion Criteria

Eligible subjects must meet/provide **all** of the following criteria:

1. Willing and able to give informed consent;
2. Willing and able to comply with the prescribed treatment protocol and evaluations for the duration of the study;
3. Adult men or women  $\geq 18$  years of age;
4. Is a recipient of a de novo kidney from a living or deceased donor and is  $>1$  year post-transplant prior to screening;
5. Is on a stable standard of care immunosuppression therapy for at least 3 months prior to screening;
6. Kidney allograft is functional at entry, based on an estimated GFR (eGFR)  $\geq 15$  mL/min/1.73m^2;
7. Women of childbearing potential have a negative screening serum pregnancy test and will be required to use a medically approved form of birth control during their participation in the study;
8. Uncontrolled gout, defined as:
  - A. Hyperuricemia during screening as documented by sUA  $\geq 7$  mg/dL during Screening and prior to entry into the Treatment Period (Note: the sUA may be repeated up to 3 times during the Screening Period to confirm eligibility); and
  - B. Inability to maintain sUA  $<6$  mg/dL on other urate-lowering therapy or intolerable side effects or contraindicated with conventional urate-lowering therapy; and
  - C. At least 1 of the following:
    - i. Evidence of tophaceous deposits;
    - ii. Recurrent gout flares defined as 2 or more flares in the past 12 months prior to Screening;
    - iii. Presence of chronic gouty arthritis; and
9. Able to tolerate low-dose prednisone ( $<10$  mg/day) as part of the required standard gout flare prophylaxis regimen for  $\geq 1$  week before the first infusion.

### 9.3.2 Exclusion Criteria

Subjects will be ineligible for study participation if they meet **any** of the following criteria:

1. Any other organ transplant beside kidney;
2. Any severe infection, unless treated and completely resolved at least 2 weeks prior to Day 1;
3. Chronic or active hepatitis B (HBV) infection;
4. Known history of hepatitis C virus RNA positivity unless treated and viral load is negative;
5. Known history of Human Immunodeficiency Virus (HIV) positivity;
6. Glucose-6-phosphate dehydrogenase (G6PD) deficiency (tested at the Screening Visit);
7. Decompensated congestive heart failure or hospitalization for congestive heart failure within 3 months of the Screening Visit, uncontrolled arrhythmia, treatment for acute coronary syndrome (myocardial infarction or unstable angina), or uncontrolled blood pressure (>160/100 mmHg) at the end of the Screening Period (Day 1 prior to infusion);
8. Pregnant, planning to become pregnant, breastfeeding, planning to impregnate female partner, or not on an effective form of birth control, as determined by the Investigator;
9. Prior treatment with pegloticase, another recombinant uricase (rasburicase), or concomitant therapy with a polyethylene glycol-conjugated drug;
10. Known allergy to pegylated products or history of anaphylactic reaction to a recombinant protein or porcine product;
11. Receipt of an investigational drug within 4 weeks or 5 half-lives, whichever is longer, prior to Day 1 or plans to take an investigational drug during the study;
12. Currently receiving systemic or radiologic treatment for ongoing cancer;
13. History of malignancy within 5 years other than non-melanoma skin cancer, in situ carcinoma of cervix, early stage renal cell cancer or early stage prostate cancer that has been completely resected >2 years prior to Screening;
14. Uncontrolled hyperglycemia with a plasma glucose value >240 mg/dL at Screening that is not subsequently controlled by the end of the Screening Period;
15. Diagnosis of osteomyelitis;
16. Known history of hypoxanthine-guanine phosphoribosyl-transferase deficiency, such as Lesch-Nyhan and Kelley-Seegmiller syndrome;
17. Unsuitable candidate for the study, based on the opinion of the Investigator (e.g., cognitive impairment), such that participation might create undue risk to the subject or interfere with the subject's ability to comply with the protocol requirements or complete the study;
18. Currently receiving allopurinol, febuxostat or other urate lowering medications and unable to discontinue medication 7 days prior to Day 1; or

19. Currently receiving probenecid and unable to discontinue medication within 3 days, prior to Day 1.

### **9.3.3 Removal of Subjects From Therapy or Study**

All subjects are free to withdraw from study participation at any time, for any reason, and without prejudice to their further medical care. In addition, the Investigator may terminate a subject from the study at any time. However, subjects who are removed from pegloticase therapy should remain on study barring withdrawal of consent for study participation.

#### **9.3.3.1 Removal of Subjects From Pegloticase Therapy**

In addition to completion of therapy through Week 24, the reason for discontinuation from the therapy should be recorded on the eCRF using 1 of the following categories:

- Lack of Efficacy: (i.e., sUA level >6 mg/dL at 2 consecutive study visits beginning with the Week 2 Visit);
- Adverse Event: The subject experiences an AE that imposes an unacceptable risk to the subject's health (e.g., anaphylactic reaction), or the subject is unwilling to continue therapy because of an AE. Subjects who discontinue treatment due to an AE should be followed until resolution or stabilization of the AE, or an adequate explanation for the event is obtained;
- Physician decision: The Investigator has determined that pegloticase administration poses an unacceptable risk to the subject (specify reason);
- Withdrawal by subject (specify reason);
- Lost to Follow-up: The subject does not return to the clinic for scheduled assessments, and does not respond to the site's attempts to contact the subject;
- Study Terminated by Sponsor: The Sponsor, IRB, or regulatory agency terminates the study;
- Pregnancy; and
- Death

##### **9.3.3.1.1 Study considerations for subjects ending pegloticase infusions prior to 24 weeks**

- All subjects will remain on study through Week 24 regardless of whether they stop infusions due to sUA stopping rules or other reason (e.g., withdrawal of consent for pegloticase infusions).
- Subjects are encouraged to continue to participate in all visits through the end of the study. Subjects are especially encouraged to complete study visits at the study site during key efficacy and safety collections at Weeks 20, 21, 22, 23, and 24 so that sUA labs and other key assessments can be completed. During visits between these key efficacy and safety collection visits, in subjects who have stopped infusions, subjects may complete study visits

in person or via telephone to collect AEs, concomitant medications and gout flare information.

- Activities related to pre/post infusion monitoring or medication dispensation will not be completed once a subject has stopped pegloticase infusions. These activities include:
  - Infusion reaction prophylaxis;
  - IR prophylaxis compliance;
  - Pegloticase infusion; and
  - Pegloticase PK sampling
- Re-introduction of oral ULTs should not start until after the End of Pegloticase Visit laboratory tests are collected.

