#### **Criteria for Evaluation:**

Efficacy will be assessed by sUA levels, tophus resolution, tophus size, urate deposition volume and bone erosion due to gout (determined by DECT), BP, and physician global assessment of gout.

Quality of life will be assessed using the Health Assessment Questionnaire - Disability Index (HAQ-DI),

■  
Pharmacokinetic and Anti-drug Antibody Endpoints:

- Serum concentrations of pegloticase; and
- Profile of anti-PEG and anti-uricase IgG antibodies.

Safety Endpoints:

The safety endpoints include the following:

- Overall AE/SAE profile;
  - Incidences of AESI: IRs, anaphylaxis, gout flares, cardiovascular events;
- Laboratory tests;
- Vital signs and physical examination; and
- Incidence of renal rejection (biopsy proven).

Statistical Analysis of Efficacy Parameters

The efficacy analysis will be performed using the modified intention-to-treat (mITT) population, defined as all enrolled subjects who received at least 1 dose of pegloticase. The proportion of Month 6 responders will be summarized, along with a 95% confidence interval (CI) for the proportion. The proportion of 5 mg/dL responders during Month 6 will be analyzed similarly.

A subject will be declared a non-responder if the subject had sUA level >6 mg/dL at 2 consecutive study visits beginning with the Week 2 Visit through Week 24 (for the primary endpoint) and through Week 14 (for exploratory endpoints). In addition, a subject who withdraws from study treatment for any reason after the first dose of pegloticase and prior to Month 6 (for the primary endpoint) or Month 3 (for exploratory endpoints) will be considered a non-responder if sUA values are not collected at the planned time points.

The proportion of subjects with resolution of  $\geq 1$  tophus (100% decrease in the area of at least 1 tophus) at Week 24 will be summarized along with the corresponding 95% CI. HAQ scores (Disability Index [DI], pain, and health), sUA, urate volume, tophi size, bone erosion, SBP, DBP, MAP, physician global assessment, eGFR, and UACR will be summarized at each visit with descriptive statistics. Changes from baseline will be summarized along with 95% CIs.

Special consideration may be given to subjects who discontinue the study or miss visits due to reasons related to the COVID-19 pandemic.

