## 9 INVESTIGATIONAL PLAN

### 9.1 Overall Study Design and Plan

This is a Phase 4, multi-site, open-label, efficacy and safety study of pegloticase in adult subjects with uncontrolled gout who have undergone kidney transplantation. Twenty subjects will be enrolled.

The study design will include: 1) a Screening Period, lasting up to 35 days; 2) a 24-week treatment period which includes an End-of-Study (Week 24)/Early Termination Visit; 3) a safety follow-up phone/email Visit 30 days after the last infusion; and 4) a 3-month post-treatment follow up visit.

During the Screening Period, eligibility will be confirmed.

Samples for measurement of sUA levels will be collected at the Screening Visit, prior to each infusion, 15-60 minutes after the end of each infusion and at the Week 24/End-of-Study/Early Termination Visit. Additional samples for sUA levels will be collected at non-infusion Visits at Weeks 21 and 23.

Subjects who meet all of the inclusion criteria and none of exclusion criteria during Screening will be enrolled at the Day 1 Visit to receive pegloticase 8 mg administered IV every 2 weeks from Day 1 through Week 22, inclusive. During this 24-week treatment phase, subjects who meet the stopping rule (based on elevated sUA levels, see Stopping Rule in Section 9.5.7.2) or discontinue treatment for any other reason will complete the End-of-Pegloticase-Infusions Visit procedures within 2 weeks and be encouraged to continue to participate in all visits through the end of the study. Subjects will return for regularly scheduled visits and will complete all study visit procedures with the exception of the pegloticase infusion and IR prophylaxis. After the Week 24/End-of-Study/Early Termination Visit (or End-of-Pegloticase-Infusions Visit [if applicable]), subjects should resume regular care for gout per the judgment of the treating physician, including resumption of ULT upon pegloticase discontinuation, if appropriate.

Subjects will have a 3-month Follow-up visit to assess clinical status, including sUA levels.

On days of scheduled infusions, pegloticase will be administered after all pre-dose study visit assessments have been completed. The date and start and stop times of infusion will be recorded. The date of the first dose of pegloticase is defined as Day 1. All subsequent doses and study visits will be scheduled based on the Day 1 Visit date.

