### 9.5.2 Quality of Life Assessment

The HAQ (Appendix 17.2) including the HAQ-DI, pain and health scales, will be administered at Screening and prior to the pegloticase infusion at the Day 1 Visit, the Week 6 and 14 Visit, the End-of-Pegloticase-Infusions Visit (if applicable), the Week 24/End-of-Study/Early Termination Visit, and the 3-month Post-Treatment Follow-up Visit (Section 2.1).

The HAQ-DI is a self-report functional status instrument that can be filled out by a subject in less than 5 minutes and requires 1 minute to score. The index measures disability over the past week by asking a total of 20 questions covering 8 domains of function: dressing and grooming, arising, eating, walking, hygiene, reach, grip, and usual activities. There are at least 2 questions in each domain and the 8 domains represent a comprehensive set of functional activities. The HAQ-DI is calculated by scoring the answer to each question in the HAQ from 0 to 3, with 0 representing the ability to do without any difficulty, and 3 representing inability to do. Any activity that requires assistance from another individual or requires the use of an assistive device raises a 0 or 1 score to a 2. The highest score for each of the 8 domains is summed (range from 0 to 24) and divided by 8 to yield, on a scale with 25 possible values, a Functional Disability Index with a range from 0 to 3. The disability index is based on the number of domains answered and is computed only if the subject completes answers to at least 6 domains (Bruce and Fries, 2003).

The HAQ pain scale consists of a doubly-anchored, horizontal visual analog scale (VAS), that is scored from 0 (no pain) to 100 (severe pain). Subjects are asked to rate the severity of the pain they have had because of illness in the past week by placing a vertical mark on the VAS.

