### 9.5.3 Pharmacokinetic and Anti-drug Antibody Measurements

Serum samples for PK analysis of pegloticase will be collected after the end of infusion on Day 1 (prior to discharge); prior to the pegloticase infusion and after the end of the infusion (prior to discharge) at Weeks 2, 6, 14, and 22. Additional PK samples will be collected at the Week 21 Visit, the End-of-Pegloticase-Infusions Visit (if applicable), and the Week 24/End-of-Study/Early Termination Visit.

Serum samples for evaluation of anti-PEG and anti-uricase IgG antibodies will be collected prior to the pegloticase infusion on Day 1 and at the Week 2, 6, 14, 22 Visits, the End-of-Pegloticase-Infusions Visit (if applicable), the Week 24/End-of-Study/Early Termination Visit, and the 3-month Post-Treatment Follow-up Visit.

Each sample collection date and time will be recorded in source documents and the eCRF.

Detailed instructions regarding blood sample timing and handling are provided in the Laboratory Manual.

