### 9.5.7.3 End-of-Pegloticase-Infusion Visit

Subjects who end pegloticase infusions prior to Week 24 will complete the End-of-Pegloticase-Infusion Visit procedures following their final infusion. Subjects should continue to participate in all visits through the end of the study. Subjects must complete selected study visits at the study site during key efficacy and safety collections at Weeks 12, 14, 20, 21, 22, 23, and 24, so that sUA labs and other key assessments can be completed. During visits between these key efficacy and safety collection visits in subjects who have stopped infusions, subjects may complete study visits in person or via a telephone visit option to collect AEs, conmeds and gout flare information (See Section 9.3.3.1.1).

The following procedures will be completed at the End-of-Pegloticase-Infusions Visit:

- [REDACTED]
- Perform a targeted physical examination (at a minimum this should include heart, lungs and abdomen);
- Record vital signs (BP, respiratory rate, temperature, and heart rate) prior to the pegloticase infusion and any time after the end of the infusion, but prior to discharge (see Section 9.5.4.4). [REDACTED]  
[REDACTED]  
[REDACTED]  
[REDACTED]  
[REDACTED]
- Record weight;
- Administer HAQ [REDACTED]
- Administer subject self-reported gout flare assessment questionnaire;
- Investigator review of clinical status and subject treatment goals;
- Ask Yes/No question regarding gout flare prophylaxis compliance;
- [REDACTED]  
[REDACTED]  
[REDACTED]  
[REDACTED]
- Obtain a urine sample from all females of childbearing potential for performance of a pregnancy test;
- Obtain blood samples for hematology and clinical chemistry analysis;
- Obtain a urine sample for albumin:creatinine ratio;
- Obtain blood and urine samples for allantoin;

- Obtain blood samples for pegloticase PK analysis;
- Obtain blood samples for anti-PEG and anti-uricase IgG antibodies;
- Obtain whole blood and serum samples for potential analyses of biomarkers from consenting subjects;
- Obtain a blood sample (1 sample) for measurement of sUA; and
- If hand held device is provided, perform fingerstick for uric acid measurement;
- Inquire about AEs and concomitant medication use.

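### Protocol Sections 9.3.3.1.1 and 9.5.7.3 contradict each other on which visits early stoppers attend on site, so Week 14 data can be lost selectively in subjects who stopped pegloticase

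*Protocol*

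**What the plan says.** Attendance after early stopping is described in three places.

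- **General text** (protocol 9.1, repeated in the synopsis, schedule footnote 2 and the SAP). Stopped subjects are encouraged to take part in all visits. The next sentence is firmer: "Subjects will return for regularly scheduled visits and will complete all study visit procedures with the exception of the pegloticase infusion and IR prophylaxis".
- **Protocol 9.3.3.1.1.** Anyone who has stopped is "especially encouraged to complete study visits at the study site during key efficacy and safety collections at Weeks 20, 21, 22, 23, and 24". Visits between these may be done "in person or via telephone to collect AEs, concomitant medications and gout flare information".
- **Protocol 9.5.7.3.** "Subjects must complete selected study visits at the study site during key efficacy and safety collections at Weeks 12, 14, 20, 21, 22, 23", and also Week 24. Visits between these may be by telephone, with a reference back to 9.3.3.1.1.

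Schedule footnote 3, in both protocol and SAP, sends the reader to 9.3.3.1.1 for the details of visits and procedures.

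Week 14 is a main assessment visit. The HAQ is given "prior to the pegloticase infusion at the Day 1 Visit, the Week 6 and 14 Visit" (protocol 9.5.2). Antibody samples are taken "prior to the pegloticase infusion on Day 1 and at the Week 2, 6, 14, 22 Visits" (9.5.3). Chemistry with eGFR and the urine albumin:creatinine ratio are also due then (9.5.4.7), as is sUA.

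For response, the synopsis makes a subject a non-responder after two consecutive sUA values above 6 mg/dL, counted through Week 14 for exploratory endpoints. A subject who withdraws from treatment before Month 6 "or Month 3 (for exploratory endpoints) will be considered a non-responder if sUA values are not collected at the planned time points".

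**The concern.** Two sections written for the same subjects give different week lists and different levels of obligation. The schedule points sites to the weaker of the two. A site that reads only 9.3.3.1.1 can reasonably telephone a stopped subject at Weeks 12 and 14, and a telephone contact yields adverse events, medications and flares but no samples and no HAQ.

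Any loss would fall only on subjects who stopped, and many of those will have stopped because they lost urate control. Protocol 7.1.2 links loss of response to high antibody titers, and 7.2 makes suppression of antibodies part of the study rationale. Week 14 antibody, renal and HAQ results would then be missing in the subjects whose results are likely to differ most from the rest.

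**Working it through.** No figure in the plan bears directly on this point. The plan's one sample-size figure, a lower 95% limit of about 46% for 14/20, is reproduced by Clopper-Pearson as 45.7%. It concerns Month 6 and is unchanged by anything below.

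**1. The rules side by side**

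| Source | On-site weeks after stopping | Obligation | Telephone |
|---|---|---|---|
| 9.1, synopsis, footnote 2, SAP | all scheduled visits | encouraged, then stated as will | not mentioned |
| 9.3.3.1.1 | 20, 21, 22, 23, 24 | encouraged | visits between these |
| 9.5.7.3 | 12, 14, 20, 21, 22, 23, 24 | must | visits between these |

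**2. Does 9.3.3.1.1 reach Weeks 12 and 14?** Read literally, its telephone sentence covers visits between Weeks 20, 21, 22, 23 and 24. The schedule has no such visits, so the sentence has an effect only if it covers earlier weeks. In 9.5.7.3 the same wording does have content, because Weeks 16 and 18 lie between Weeks 14 and 20. A likely inference is that Weeks 12 and 14 are missing from the 9.3.3.1.1 list.

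**3. Who would have no Week 14 value?** The End-of-Pegloticase visit collects HAQ, chemistry, urine albumin:creatinine ratio, antibodies and sUA (9.5.7.3). SAP 8.4 moves it into a scheduled slot that is otherwise empty. Inputs:

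- infusion day at Week w = 1 + 7w
- End-of-Pegloticase visit 1 to 14 days after the last infusion (footnote 3: within 2 weeks)
- Week 14 window: Days 72–120 for HAQ (SAP Table 4), Days 72–127 for laboratory and antibody data (Table 3)

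Results:

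- Last infusion at Week 12 (Day 85): visit on Days 86–99, fills Week 14.
- Last infusion at Week 10 (Day 71): visit on Days 72–85, fills Week 14.
- Last infusion at Week 8 (Day 57): visit on Days 58–71, falls in Week 6. A Week 8 infusion given 3 days late could push the visit to Day 57 + 3 + 14 = 74 and fill Week 14.
- Last infusion on Day 1 to Week 6 (Day 43 at the latest): visit by Day 57, does not reach Week 14.

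For HAQ, laboratory and antibody data, the exposed group is therefore mainly subjects whose last infusion was on Day 1 to Week 8.

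For sUA the Week 14 window is narrower, Days 93–106 (Table 1). Only a last infusion at Week 12, with the visit on Days 93–99, would fill it.

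**4. Size.** The documents do not give the number of such early stoppers. Each one is 1/20 = 5% of the planned sample. As an assumption only, 1 to 6 of them would leave 5% to 30% of subjects without Week 14 values.

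**5. Which analyses are exposed?**

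- HAQ: the 'Overall' Week 14 summaries (SAP 10.3.2, 10.3.3). The 'On Treatment' summaries leave out later post-stop visits by design.
- Laboratory data: the 'Overall' and 'Post-Treatment' summaries (SAP 12.4).
- Antibodies: incidence by timepoint and Kaplan-Meier time to positivity (SAP 11). By default, percentages use subjects with an observation as denominator (SAP 16.2.5.2), so missing stoppers leave the denominator.
- Month 3 response: a subject with two consecutive values above 6 mg/dL is already a non-responder. For any other treatment withdrawal, the synopsis makes uncollected sUA a non-response and leaves collected sUA to be scored. Only there can the result depend on which section the site followed.

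**The case against.** The strongest reply is that this is a small wording mismatch. The general text already encourages all visits, 9.3.3.1.1 keeps the in-person option and never names Weeks 12 or 14, and most of the consequences can be traced and bounded. Much of that stands.

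Four stronger readings are tempting, and the documents do not support them.

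- **That Week 14 data will go missing.** The text permits the loss. It does not cause it.
- **That Month 3 response is broadly compromised.** Stopping-rule subjects are classified whatever is collected later. The SAP's exploratory text is redacted, so the effect on the actual Month 3 analysis cannot be checked.
- **That graft chemistry may lapse for 18 weeks,** from an End-of-Pegloticase visit at Week 4 to Week 22. This overlooks the 3-month follow-up, which also collects chemistry (9.5.7.6). With 3 months taken as about 13 weeks and a last infusion at Week 2, it falls near Week 2 + 13 = 15 (synopsis, counted from the last infusion) or Week 4 + 13 = 17 (footnote 4, counted from the End-of-Pegloticase visit). The gap is then 11 to 13 weeks, against 10 under 9.5.7.3. The protocol says a follow-up visit falling before Week 24 will be adjusted, without saying how, so neither figure is firm. Biopsy-confirmed rejection is recorded through adverse events, which telephone contacts still collect.
- **That the main efficacy results are at risk.** The primary and 5 mg/dL endpoints use Weeks 20 to 24, and the secondary HAQ endpoints use Week 24. Both sections name those weeks as on-site visits.

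What the reply does not remove is the contradiction itself, or the fact that the schedule sends sites to the section with the weaker rule.

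**Conclusion.** The point holds in limited form. Sections 9.3.3.1.1 and 9.5.7.3 conflict on both the week list and the obligation, and the general text does not settle it. A site may follow the protocol and still collect no Week 14 sUA, HAQ, antibody, chemistry or urine albumin:creatinine data in a subject who has stopped.

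This rests on the natural rather than the literal reading of the telephone sentence, and the window calculation assumes on-time infusions and an End-of-Pegloticase visit within 14 days. The harm is possible selective missingness in descriptive Week 14 summaries that include stopped subjects, plus Month 3 classification for the few withdrawals outside the stopping rule. It should be corrected because, with 20 subjects, a handful of early stoppers is a visible share of any summary and the correction is cheap.

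**What to change.** - In 9.3.3.1.1, replace the week list with that of 9.5.7.3 (on site at Weeks 12, 14, 20, 21, 22, 23 and 24), and use one level of obligation in both sections.
- Limit the telephone option to the remaining visits, named explicitly rather than as visits in between.
- Leave the all-procedures sentence in 9.1, the synopsis and footnote 2 as it is, adding only a cross-reference. Replacing it with the 9.5.7.3 list would remove the Week 6 assessments that this text now calls for in early stoppers.
- State whether scheduled Week 6 assessments are on site for a subject who has already stopped, since neither week list includes Week 6.
- Align the matching SAP text.

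The cost is a wording change in an amendment. It adds no visit beyond those that the general text and 9.5.7.3 already call for. The downside is that early stoppers lose the telephone option at Weeks 12 and 14. Sample size and the 14/20 criterion do not change.
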